11.1.2 Disease Parameters

Measurable disease. Measurable lesions are defined as those that can be accurately measured in at least one dimension (longest diameter to be recorded) as ≥ 20 mm by chest x-ray or as ≥ 10 mm with CT scan, MRI, or calipers by clinical exam. All tumor measurements must be recorded in millimeters (or decimal fractions of centimeters).

Note: Tumor lesions that are situated in a previously irradiated area might or might not be considered measurable. *If the investigator thinks it appropriate to include them, the conditions under which such lesions should be considered must be defined in the protocol.*

Malignant lymph nodes. To be considered pathologically enlarged and measurable, a lymph node must be ≥ 15 mm in short axis when assessed by CT scan (CT scan slice thickness recommended to be no greater than 5 mm). At baseline and in follow-up, only the short axis will be measured and followed.

Non-measurable disease. All other lesions (or sites of disease), including small lesions (longest diameter < 10 mm or pathological lymph nodes with ≥ 10 to < 15 mm short axis), are considered non-measurable disease. Bone lesions, leptomeningeal disease, ascites, pleural/pericardial effusions, lymphangitis cutis/pulmonitis, inflammatory breast disease, and abdominal masses (not followed by CT or MRI), are considered as non-measurable.

Note: Cystic lesions that meet the criteria for radiographically defined simple cysts should not be considered as malignant lesions (neither measurable nor non-measurable) since they are, by definition, simple cysts.

'Cystic lesions' thought to represent cystic metastases can be considered as measurable lesions, if they meet the definition of measurability described above. However, if non-cystic lesions are present in the same patient, these are preferred for selection as target lesions.

Target lesions. All measurable lesions up to a maximum of 2 lesions per organ and 5 lesions in total, representative of all involved organs, should be identified as **target lesions** and recorded and measured at baseline. Target lesions should be selected on the basis of their size (lesions with the longest diameter), be representative of all involved organs, but in addition should be those that lend themselves to reproducible repeated measurements. It may be the case that, on occasion, the largest lesion does not lend itself to reproducible measurement in which circumstance the next largest lesion which can be measured reproducibly should be selected. A sum of the diameters (longest for non-nodal lesions, short axis for nodal lesions) for all target lesions will be calculated and reported as the baseline sum diameters. If lymph nodes are to be included in the sum, then only the short axis is added into the sum. The baseline sum diameters will be used as reference to further characterize any objective tumor regression in the measurable dimension of the disease.

Non-target lesions. All other lesions (or sites of disease) including any measurable lesions over and above the 5 target lesions should be identified as **non-target lesions** and should also be recorded at baseline. Measurements of these lesions are not required, but the presence, absence, or in rare cases unequivocal progression of each should be noted throughout follow-up.

11.1.3 Methods for Evaluation of Measurable Disease

All measurements should be taken and recorded in metric notation using a ruler or calipers. All baseline evaluations should be performed as closely as possible to the beginning of treatment and never more than 4 weeks before the beginning of the treatment.

The same method of assessment and the same technique should be used to characterize each identified and reported lesion at baseline and during follow-up. Imaging-based evaluation is preferred to evaluation by clinical examination unless the lesion(s) being followed cannot be imaged but are assessable by clinical exam.

Clinical lesions Clinical lesions will only be considered measurable when they are superficial (e.g., skin nodules and palpable lymph nodes) and ≥ 10 mm diameter as assessed using calipers (e.g., skin nodules). In the case of skin lesions, documentation by color photography, including a ruler to estimate the size of the lesion, is recommended. In the case that skin lesions are followed, documentation of pathologic CR of that lesion will be made via biopsy in the event that a previously raised lesion becomes flat.

Chest x-ray Lesions on chest x-ray are acceptable as measurable lesions when they are clearly defined and surrounded by aerated lung. However, CT is preferable.

Conventional CT and MRI This guideline has defined measurability of lesions on CT scan based on the assumption that CT slice thickness is 5 mm or less. If CT scans have slice thickness greater than 5 mm, the minimum size for a measurable lesion should be twice the slice thickness. MRI is also acceptable in certain situations (e.g. for body scans).

Use of MRI remains a complex issue. MRI has excellent contrast, spatial, and temporal resolution; however, there are many image acquisition variables involved in MRI, which greatly impact image quality, lesion conspicuity, and measurement. Furthermore, the availability of MRI is variable globally. As with CT, if an MRI is performed, the technical specifications of the scanning sequences used should be optimized for the evaluation of the type and site of disease. Furthermore, as with CT, the modality used at follow-up should be the same as was used at baseline and the lesions should be measured/assessed on the same pulse sequence. It is beyond the scope of the RECIST guidelines to prescribe specific MRI pulse sequence parameters for all scanners, body parts, and diseases. Ideally, the same type of scanner should be used and the image acquisition protocol should be followed as closely as possible to prior scans. Body scans should be performed with breath-hold scanning techniques, if possible.

PET-CT At present, the low dose or attenuation correction CT portion of a combined PET-CT is not always of optimal diagnostic CT quality for use with RECIST measurements. However, if the site can document that the CT performed as part of a PET-CT is of identical diagnostic quality to a diagnostic CT (with IV and oral contrast), then the CT portion of the PET-CT can be used for RECIST measurements and can be

used interchangeably with conventional CT in accurately measuring cancer lesions over time. Note, however, that the PET portion of the CT introduces additional data which may bias an investigator if it is not routinely or serially performed.

Ultrasound Ultrasound is not useful in assessment of lesion size and should not be used as a method of measurement. Ultrasound examinations cannot be reproduced in their entirety for independent review at a later date and, because they are operator dependent, it cannot be guaranteed that the same technique and measurements will be taken from one assessment to the next. If new lesions are identified by ultrasound in the course of the study, confirmation by CT or MRI is advised. If there is concern about radiation exposure at CT, MRI may be used instead of CT in selected instances.

Endoscopy, Laparoscopy The utilization of these techniques for objective tumor evaluation is not advised. However, such techniques may be useful to confirm complete pathological response when biopsies are obtained or to determine relapse in trials where recurrence following complete response (CR) or surgical resection is an endpoint.

Tumor markers Tumor markers alone cannot be used to assess response. If markers are initially above the upper normal limit, they must normalize for a patient to be considered in complete clinical response. Specific guidelines for both CA-125 response (in recurrent ovarian cancer) and PSA response (in recurrent prostate cancer) have been published [JNCI 96:487-488, 2004; J Clin Oncol 17, 3461-3467, 1999; J Clin Oncol 26:1148-1159, 2008]. In addition, the Gynecologic Cancer Intergroup has developed CA-125 progression criteria which are to be integrated with objective tumor assessment for use in first-line trials in ovarian cancer [JNCI 92:1534-1535, 2000].

Cytology, Histology These techniques can be used to differentiate between partial responses (PR) and complete responses (CR) in rare cases (e.g., residual lesions in tumor types, such as germ cell tumors, where known residual benign tumors can remain).

The cytological confirmation of the neoplastic origin of any effusion that appears or worsens during treatment when the measurable tumor has met criteria for response or stable disease is mandatory to differentiate between response or stable disease (an effusion may be a side effect of the treatment) and progressive disease.

FDG-PET While FDG-PET response assessments need additional study, it is sometimes reasonable to incorporate the use of FDG-PET scanning to complement CT scanning in assessment of progression (particularly possible 'new' disease). New lesions on the basis of FDG-PET imaging can be identified according to the following algorithm:

- a. Negative FDG-PET at baseline, with a positive FDG-PET at follow-up is a sign of PD based on a new lesion.
- b. No FDG-PET at baseline and a positive FDG-PET at follow-up: If the positive FDG-PET at follow-up corresponds to a new site of disease confirmed by CT, this is PD. If the positive FDG-PET at follow-up is not confirmed as a new site of disease on CT, additional follow-up CT scans are needed to determine if there is truly progression occurring at that site (if so, the date of PD will be the date of the initial abnormal FDG-PET scan). If the positive FDG-PET at follow-up corresponds to a pre-existing

site of disease on CT that is not progressing on the basis of the anatomic images, this is not PD.

- c. FDG-PET may be used to upgrade a response to a CR in a manner similar to a biopsy in cases where a residual radiographic abnormality is thought to represent fibrosis or scarring. The use of FDG-PET in this circumstance should be prospectively described in the protocol and supported by disease-specific medical literature for the indication. However, it must be acknowledged that both approaches may lead to false positive CR due to limitations of FDG-PET and biopsy resolution/sensitivity.

Note: A 'positive' FDG-PET scan lesion means one which is FDG avid with an uptake greater than twice that of the surrounding tissue on the attenuation corrected image.

11.1.4 Response Criteria

11.1.4.1 Evaluation of Target Lesions

Complete Response (CR): Disappearance of all target lesions. Any pathological lymph nodes (whether target or non-target) must have reduction in short axis to <10 mm.

Partial Response (PR): At least a 30% decrease in the sum of the diameters of target lesions, taking as reference the baseline sum diameters.

Progressive Disease (PD): At least a 20% increase in the sum of the diameters of target lesions, taking as reference the smallest sum on study (this includes the baseline sum if that is the smallest on study). In addition to the relative increase of 20%, the sum must also demonstrate an absolute increase of at least 5 mm. (Note: the appearance of one or more new lesions is also considered progressions).

Stable Disease (SD): Neither sufficient shrinkage to qualify for PR nor sufficient increase to qualify for PD, taking as reference the smallest sum diameters while on study.

11.1.4.2 Evaluation of Non-Target Lesions

Complete Response (CR): Disappearance of all non-target lesions and normalization of tumor marker level. All lymph nodes must be non-pathological in size (<10 mm short axis).

Note: If tumor markers are initially above the upper normal limit, they must normalize for a patient to be considered in complete clinical response.

Non-CR/Non-PD: Persistence of one or more non-target lesion(s) and/or maintenance of tumor marker level above the normal limits.

Progressive Disease (PD): Appearance of one or more new lesions and/or

unequivocal progression of existing non-target lesions. *Unequivocal progression* should not normally trump target lesion status. It must be representative of overall disease status change, not a single lesion increase.

Although a clear progression of “non-target” lesions only is exceptional, the opinion of the treating physician should prevail in such circumstances, and the progression status should be confirmed at a later time by the review panel (or Principal Investigator).

11.1.4.3 Evaluation of Best Overall Response

The best overall response is the best response recorded from the start of the treatment until disease progression/recurrence (taking as reference for progressive disease the smallest measurements recorded since the treatment started). The patient's best response assignment will depend on the achievement of both measurement and confirmation criteria.

For Patients with Measurable Disease (*i.e.*, Target Disease)

Target Lesions	Non-Target Lesions	New Lesions	Overall Response	Best Overall Response when Confirmation is Required*
CR	CR	No	CR	≥ 4 wks. Confirmation**
CR	Non-CR/Non-PD	No	PR	≥ 4 wks. Confirmation**
CR	Not evaluated	No	PR	
PR	Non-CR/Non-PD/not evaluated	No	PR	Documented at least once ≥ 4 wks. from baseline**
SD	Non-CR/Non-PD/not evaluated	No	SD	
PD	Any	Yes or No	PD	no prior SD, PR or CR
Any	PD***	Yes or No	PD	
Any	Any	Yes	PD	

* See RECIST 1.1 manuscript for further details on what is evidence of a new lesion.

** Only for non-randomized trials with response as primary endpoint.

*** In exceptional circumstances, unequivocal progression in non-target lesions may be accepted as disease progression.

Note: Patients with a global deterioration of health status requiring discontinuation of treatment without objective evidence of disease progression at that time should be reported as “*symptomatic deterioration*.” Every effort should be made to document the objective progression even after discontinuation of treatment.

For Patients with Non-Measurable Disease (*i.e.*, Non-Target Disease)

Non-Target Lesions	New Lesions	Overall Response
CR	No	CR
Non-CR/non-PD	No	Non-CR/non-PD*
Not all evaluated	No	not evaluated
Unequivocal PD	Yes or No	PD
Any	Yes	PD

* ‘Non-CR/non-PD’ is preferred over ‘stable disease’ for non-target disease since SD is increasingly used as an endpoint for assessment of efficacy in some trials so to assign this category when no lesions can be measured is not advised

11.1.5 Duration of Response

Duration of overall response: The duration of overall response is measured from the time measurement criteria are met for CR or PR (whichever is first recorded) until the first date that recurrent or progressive disease is objectively documented (taking as reference for progressive disease the smallest measurements recorded since the treatment started).

The duration of overall CR is measured from the time measurement criteria are first met for CR until the first date that progressive disease is objectively documented.

Duration of stable disease: Stable disease is measured from the start of the treatment until the criteria for progression are met, taking as reference the smallest measurements recorded since the treatment started, including the baseline measurements.

11.1.6 Progression-Free Survival

PFS is defined as the duration of time from start of treatment to time of progression or death, whichever occurs first.

12. DATA REPORTING / REGULATORY REQUIREMENTS

Adverse event lists, guidelines, and instructions for AE reporting can be found in Section 7.0 (Adverse Events: List and Reporting Requirements).

12.1 Data Reporting

12.1.1 Method

This study will be monitored by the Clinical Trials Monitoring Service (CTMS). Information on CTMS reporting is available at <http://www.theradex.com/CTMS>. Data collection for this study will be done exclusively through Medidata Rave. Data will be submitted by all participating institutions to CTMS at least once every two weeks via Medidata Rave.

Users that have not previously activated their iMedidata/Rave account will receive a separate invitation from iMedidata to activate their account. Account activation instructions are located on the CTSU web site, Rave tab under Rave resource materials (Medidata Account Activation and Study Invitation Acceptance). Additional information on iMedidata/Rave is available on the CTSU website under the Rave tab at <http://[contact]>. For CTMS monitored studies, after users have activated their accounts, please contact the Theradex Help Desk at [contact] or by email at [contact] for additional support with Rave and completion of CRFs.

12.1.2 Responsibility for Data Submission

Study participants are responsible for submitting data every two weeks to CTMS via Medidata Rave.

12.2 CTEP Multicenter Guidelines

This protocol will adhere to the policies and requirements of the CTEP Multicenter Guidelines. The specific responsibilities of the Principal Investigator and the Coordinating Center (Study Coordinator) and the procedures for auditing are presented in Appendix B.

- The Principal Investigator/Coordinating Center is responsible for distributing all IND Action Letters or Safety Reports received from CTEP to all participating institutions for submission to their individual IRBs for action as required.
- Except in very unusual circumstances, each participating institution will order DCTD-supplied agents directly from CTEP. Agents may be ordered by a participating site only after the initial IRB approval for the site has been forwarded by the Coordinating Center to the CTEP PIO ([contact]) except for Group studies.

12.3 Collaborative Agreements Language

The agent(s) supplied by CTEP, DCTD, NCI used in this protocol is/are provided to the NCI under a Collaborative Agreement (CRADA, CTA, CSA) between the Pharmaceutical Company(ies) (hereinafter referred to as “Collaborator(s)”) and the NCI Division of Cancer Treatment and Diagnosis. Therefore, the following obligations/guidelines, in addition to the provisions in the “Intellectual Property Option to Collaborator” (http://ctep.cancer.gov/industryCollaborations2/intellectual_property.htm) contained within the terms of award, apply to the use of the Agent(s) in this study:

1. Agent(s) may not be used for any purpose outside the scope of this protocol, nor can Agent(s) be transferred or licensed to any party not participating in the clinical study. Collaborator(s) data for Agent(s) are confidential and proprietary to Collaborator(s) and shall be maintained as such by the investigators. The protocol documents for studies utilizing Agents contain confidential information and should not be shared or distributed without the permission of the NCI. If a copy of this protocol is requested by a patient or patient’s family member participating on the study, the individual should sign a confidentiality agreement. A

suitable model agreement can be downloaded from: <http://ctep.cancer.gov>.

2. For a clinical protocol where there is an investigational Agent used in combination with (an)other Agent(s), each the subject of different Collaborative Agreements, the access to and use of data by each Collaborator shall be as follows (data pertaining to such combination use shall hereinafter be referred to as "Multi-Party Data"):
 - a. NCI will provide all Collaborators with prior written notice regarding the existence and nature of any agreements governing their collaboration with NCI, the design of the proposed combination protocol, and the existence of any obligations that would tend to restrict NCI's participation in the proposed combination protocol.
 - b. Each Collaborator shall agree to permit use of the Multi-Party Data from the clinical trial by any other Collaborator solely to the extent necessary to allow said other Collaborator to develop, obtain regulatory approval or commercialize its own Agent.
 - c. Any Collaborator having the right to use the Multi-Party Data from these trials must agree in writing prior to the commencement of the trials that it will use the Multi-Party Data solely for development, regulatory approval, and commercialization of its own Agent.
3. Clinical Trial Data and Results and Raw Data developed under a Collaborative Agreement will be made available to Collaborator(s), the NCI, and the FDA, as appropriate and unless additional disclosure is required by law or court order as described in the IP Option to Collaborator (http://ctep.cancer.gov/industryCollaborations2/intellectual_property.htm). Additionally, all Clinical Data and Results and Raw Data will be collected, used and disclosed consistent with all applicable federal statutes and regulations for the protection of human subjects, including, if applicable, the *Standards for Privacy of Individually Identifiable Health Information* set forth in 45 C.F.R. Part 164.
4. When a Collaborator wishes to initiate a data request, the request should first be sent to the NCI, who will then notify the appropriate investigators (Group Chair for Cooperative Group studies, or PI for other studies) of Collaborator's wish to contact them.
5. Any data provided to Collaborator(s) for Phase 3 studies must be in accordance with the guidelines and policies of the responsible Data Monitoring Committee (DMC), if there is a DMC for this clinical trial.
6. Any manuscripts reporting the results of this clinical trial must be provided to CTEP by the Group office for Cooperative Group studies or by the principal investigator for non-Cooperative Group studies for immediate delivery to Collaborator(s) for advisory review and comment prior to submission for publication. Collaborator(s) will have 30 days from the date of receipt for review. Collaborator shall have the right to request that publication be delayed for up to an additional 30 days in order to ensure that Collaborator's confidential and proprietary data, in addition to Collaborator(s)'s intellectual property rights, are protected. Copies of abstracts must be provided to CTEP for forwarding to Collaborator(s) for courtesy

review as soon as possible and preferably at least three (3) days prior to submission, but in any case, prior to presentation at the meeting or publication in the proceedings. Press releases and other media presentations must also be forwarded to CTEP prior to release. Copies of any manuscript, abstract and/or press release/ media presentation should be sent to:

Email: [contact]

The Regulatory Affairs Branch will then distribute them to Collaborator(s). No publication, manuscript or other form of public disclosure shall contain any of Collaborator's confidential/ proprietary information.

13. STATISTICAL CONSIDERATIONS

13.1 Study Design/Endpoints

This is a phase I trial of the combination of dabrafenib, trametinib, and AT13387 in patients with BRAF-mutant advanced solid tumors. The primary objective of the study is to determine the maximum tolerated dose (MTD) of the combination; secondary objectives will provide preliminary estimates of efficacy and toxicity. The escalation and stopping rules imply that the incidence rate for DLT will be less than 33% at the MTD. Following the identification of the MTD, an additional 14 patients will be enrolled in a dose expansion cohort at the MTD.

Toxicities and lab values will be graded according to the NCI Common Toxicity Criteria for Adverse Events (v4.0). Dose-limiting toxicities will be scored and will be defined as in Section 5.2.

Dose escalation will use a standard “3+3” approach, beginning in dose level 1, with dosing and rules for escalation and de-escalation described in the tables below. Tolerability assessments will be based on cycle 1 alone. The MTD is defined as the highest dose level at which 0 or 1 of six patients has experienced a DLT. If an excessive number of toxicities occur at the initial dose level 1, the dose will be reduced to the fall-back dose of -1. If dose level -1 has excessive toxicity, the study will stop.

Dose Level	Dabrafenib [BID/PO]	Trametinib [QD/PO]	AT13387 [D1,8,15/IV]
-1	75 mg	1 mg	180 mg/m ²
1	150 mg	1 mg	180 mg/m ²
2	150 mg	2 mg	180 mg/m ²
3	150 mg	2 mg	220 mg/m ²
4	150 mg	2 mg	260 mg/m ²

Number of Patients with DLT at a Given Dose Level	Dose Escalation Rule
0 out of 3	Proceed to the next dose level and enroll 3 patients
1 out of 3	Enroll and treat 3 additional patients at this dose level
	Dose escalation will be stopped. The MTD will be one dose below this dose

≥ 2 out of 3	level. Three (3) additional patients will be entered at the next lower dose level if only 3 patients were treated previously at that dose.
1 out of 6	Proceed to the next dose level.
≥ 2 out of 6	se escalation will be stopped. The MTD will be one dose below this dose level. Three (3) additional patients will be entered at the next lower dose level if only 3 patients were treated previously at that dose.
If $\geq 2/3$ or $\geq 2/6$ patients at dose level 1 experience dose limiting toxicities, dose level -1 will be enrolled. If dose level -1 proves too toxic, the study will stop.	Dose escalation will be stopped. The MTD will be one dose below this dose level. Three (3) additional patients will be entered at the next lower dose level if only 3 patients were treated previously at that dose.

The following table shows the probability of escalating the dose for various true, but unknown, rates of unacceptable toxicity.

True DLT Rate	Probability of Dose Escalation
0.10	0.91
0.20	0.71
0.30	0.49
0.40	0.31
0.50	0.17
0.60	0.08

A patient will be replaced if determination of DLT cannot be adequately assessed because of rapid disease progression or if treatment is stopped during the first cycle of therapy for reasons other than toxicity.

When the MTD had been determined, a total of 14 patients will be enrolled in an expansion cohort of patients with BRAF-mutant advanced solid tumors to obtain preliminary toxicity and efficacy estimates. Patients treated at the MTD during the dose escalation phase may be included in the expansion cohort. Toxicity and efficacy rates will be summarized with 90% exact binomial confidence intervals. For a sample of size 14, the confidence intervals will be no wider than 0.48.

The table below summarizes the probabilities of observing at least one patient with a severe or unexpected toxicity in the expansion cohort for a range of incidence rates.

True Incidence of Unexpected or Severe Toxicity	Probability of Observing One or More Patients with Toxicity among 14
0.01	0.13
0.03	0.35
0.05	0.51
0.08	0.69
0.09	0.73
0.10	0.77
0.15	0.90

Secondary endpoints that will be assessed for the 14 patients treated at the MTD are: objective response rate, progression-free survival (PFS), 6-month PFS, and 1-year overall survival (OS).

Objective response rate is defined as the proportion of patients with complete or partial response as their best response to therapy. At the time of each restaging, patients will be classified as achieving complete response (CR), partial response (PR), stable disease (SD), progressive disease (PD), or non-evaluable for response according to RECIST (Version 1.1) criteria. Objective response will be determined by the best overall response designation recorded between the date of first dose of trial therapy and the date of objectively documented disease progression or cessation of trial therapy, whichever occurs first. For patients without documented progression or cessation of trial therapy, all available response designations will contribute to the objective response determination.

The distributions of progression-free survival (PFS) and overall survival (OS) will each be summarized using the product-limit method of Kaplan-Meier. Median times for each endpoint will be presented with two-sided, 90% confidence intervals estimated using log(-log(survival)) methodology. Kaplan-Meier estimates of 6-month PFS and 1-year OS will also be presented with two-sided, 90% confidence intervals.

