5.2 Definition of Dose Limiting Toxicity

Dose-limiting toxicity (DLT) is based on the CTEP Active Version 5 of the NCI Common Terminology Criteria for Adverse Events (CTCAE). DLT refers to toxicities experienced during the first cycle of treatment between days 1-28. A DLT must be considered to be at least possibly related to study drug(s) will be defined as follows:

- Any grade 4 toxicity
- Grade 3 (or grade 2 intolerable) non-hematologic toxicity
- Grade ≥ 3 neutropenia with fever $> 38.5^{\circ}\text{C}$
- Grade 3 thrombocytopenia with clinically significant bleeding
- Furthermore, grade 2 intolerable/grade 3 fatigue that results in hospitalization should be considered a DLT.
- Intolerable AEs are toxicities deemed to lead to a missing dose of AT13387 or more than 25% of dabrafenib/trametinib in the first cycle.

In general, all Grade 3 or intolerable grade 2, non-hematological toxicities regardless of duration are considered DLT. However, the following Grade 3 toxicities will not be considered a DLT.

- The appearance of cutaneous squamous cell carcinoma or keratoacanthoma will not be considered a dose limiting toxicity as these are commonly observed with dabrafenib.
- Grade 3 fatigue persistent for ≤ 7 days
- Grade 3 nausea, vomiting, or diarrhea persisting ≤ 72 hours with maximum supportive care
- Grade 3 electrolyte events if they are resolved with replacement within 24 hours
- Lymphopenia regardless of grade
- The following grade 3 laboratory abnormalities will not be considered dose limiting if they return to baseline within 7 days: elevated bilirubin, AST, ALT, cholesterol, amylase, lipase, creatinine and hypertriglyceridemia

Management and dose modifications associated with the above adverse events are outlined in Section 6.

Dose escalation will proceed within each cohort according to the following scheme. Dose-limiting toxicity (DLT) is defined above.

Table 5.2. Dose escalation table

Number of Patients with DLT at a Given Dose Level	Dose Escalation Rule
0 out of 3	Proceed to the next dose level and enroll 3 patients
1 out of 3	Enroll and treat 3 additional patients at this dose level.
≥ 2 out of 3	Dose escalation will be stopped. The MTD will be one dose below this dose level. Three (3) additional patients will be entered at the next lower dose level if only 3 patients were treated previously at that dose.
1 out of 6	Proceed to the next dose level.

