13.2 Sample Size/Accrual Rate

The total enrollment of this trial will be between 4 and 32 evaluable patients. The minimum would occur if the triple combination proved too toxic at dose levels 1 and -1 and the trial was stopped during the dose escalation phase. A maximum enrollment of 32 patients reflects four complete dose escalation cohorts of 6 patients each and the expansion cohort of 14 total patients at the MTD. Assuming an accrual rate of 2-3 patients per month, we estimate a maximum enrollment period of 20 months.

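### Section 13.1 says the 3+3 rules imply a DLT incidence below 33% at the MTD, but they limit only the observed count; Section 5.2 also classifies one kind of fatigue event both ways

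*Combined protocol and SAP*

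**What the plan says.** Section 13.1 describes a standard 3+3 design and draws this conclusion from it: "The escalation and stopping rules imply that the incidence rate for DLT will be less than 33% at the MTD". Two paragraphs later it gives the criterion actually used: "The MTD is defined as the highest dose level at which 0 or 1 of six patients has experienced a DLT". It then tabulates operating characteristics: "The following table shows the probability of escalating the dose for various true, but unknown, rates of unacceptable toxicity". For the expansion cohort it adds: "Toxicity and efficacy rates will be summarized with 90% exact binomial confidence intervals".

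The number of patients who will finally contribute at the MTD is described in different ways. The opening paragraph of 13.1 says "an additional 14 patients will be enrolled in a dose expansion cohort at the MTD". Later in 13.1: "Patients treated at the MTD during the dose escalation phase may be included in the expansion cohort". Section 13.2 refers to "the expansion cohort of 14 total patients at the MTD".

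DLTs are scored by Section 5.2. One bullet there says that "grade 2 intolerable/grade 3 fatigue that results in hospitalization should be considered a DLT", with no condition on duration. The list of exceptions in the same section removes grade 3 fatigue lasting 7 days or less, with no condition on hospitalisation.

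**The concern.** The MTD is the primary result. The sentence credits it with a property of the true DLT rate, whereas the rule constrains only a count in six patients. A reader could take it that a dose with a true rate of 33% or more cannot be declared the MTD.

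The fatigue overlap is a separate matter but feeds the same count. Grade 3 fatigue that leads to admission and resolves within a week is a DLT under one bullet and exempt under the other. In cohorts of three and six, one event separates 0/3 from 1/3, or 1/6 from 2/6.

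**Working it through.** **Inputs.** The escalation rules, the MTD definition, the escalation-probability table and the 90% exact level come from 13.1. Fatigue rates come from the adverse event tables in 2.2.2.4 and 2.2.3.4. The documents give no expected DLT rates by dose level.

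**1. The plan's own table.** A level is passed with 0/3, or with 1/3 followed by 0/3:

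P(escalate) = (1-p)^3 + 3p(1-p)^2 × (1-p)^3

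At p = 0.40 this is 0.216 + 0.093 = 0.309. For p = 0.10, 0.20, 0.30, 0.40, 0.50 and 0.60 the results are 0.906, 0.709, 0.494, 0.309, 0.172 and 0.082. All six agree with the printed 0.91, 0.71, 0.49, 0.31, 0.17 and 0.08, so the table is right and the rules have been read as intended.

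**2. Chance that a too-toxic level meets the MTD criterion.** For a level filled to six:

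P(0 or 1 of 6) = (1-p)^6 + 6p(1-p)^5

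| True DLT rate | P(0 or 1 of 6) |
|---|---|
| 1/3 | 0.088 + 0.263 = 0.351 |
| 0.40 | 0.047 + 0.187 = 0.233 |
| 0.50 | 0.016 + 0.094 = 0.109 |

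**3. What the observed count says about the true rate.** Clopper-Pearson 90% limits:

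- 0/6: upper limit 1 - 0.05^(1/6) = 0.393, so 0%-39%.
- 1/6: the upper limit solves (1-p)^6 + 6p(1-p)^5 = 0.05, giving 0.582; the lower limit is 0.009.
- After expansion with 14 patients: 1/14 has upper limit 0.297 and 2/14 has 0.385.
- After expansion with 20 patients (6 + 14): 2/20 has upper limit 0.283 and 3/20 has 0.344.

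The upper limit therefore falls below 33% only with 0-1 DLTs of 14 or 0-2 of 20. These are nominal intervals; they make no allowance for the dose having been selected on the first six patients.

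**4. Chance that the declared MTD has a true rate of 33% or more.** This needs assumed dose-toxicity curves. The first six rows are exact enumerations. The last four are simulations with the cut at 1/3. In all of them a level with 0/3 is filled to six before it can be the MTD. Percentages are of all trials.

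| Assumed true rates, levels -1, 1, 2, 3, 4 | P(true rate at MTD ≥ 33%) |
|---|---|
| .10 .15 .20 .25 .30 | 0% |
| .05 .10 .20 .32 .50 | 3% |
| .10 .20 .30 .40 .50 | 9% |
| .25 .32 .40 .45 .50 | 11% |
| .10 .20 .40 .50 .60 | 17% |
| .05 .10 .20 .35 .50 | 21% |
| .10 .15 .25 .40 .55 | 12% |
| .10 .20 .35 .45 .55 | 24% |
| .20 .35 .40 .45 .50 | 34% |
| .40 at every level | 43% |

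Over the first six curves the mean true rate at the declared MTD is 19%-30%.

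**5. Size of the fatigue overlap.** Grade 3-4 fatigue was 0 of 86 on AT13387, 2% and 4% on the two dabrafenib-trametinib arms, and 6% on dabrafenib alone. Suppose a fraction f of patients had an ambiguous event, at a level with a 20% DLT rate otherwise. Counting those events gives p = 1 - 0.80(1-f). P(escalate) falls from 0.709 to 0.674 (f = 0.02), 0.639 (f = 0.04) or 0.604 (f = 0.06). These overstate the effect at each rate, because only cycle-1 episodes with admission that last 7 days or less are ambiguous. They are not a bound for the triplet, whose fatigue rate is unknown.

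**The case against.** The strongest reply is that the sentence is only loose wording. Two of six is the stopping cut, so as a statement about the observed fraction it is true. The same section defines the MTD by an observed count, tabulates escalation at true rates up to 0.60 and plans exact intervals. The sentence drives no decision rule, and correcting it moves no patient to another dose. That much is fair and keeps the point below the most serious grade. But the sentence does not say observed, and the table that follows treats the true rate as unknown, so the text claims more than the design delivers.

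Some limits on the figures stand:

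- The 0.31 at a true rate of 0.40 is the chance of escalating past a level. It is not the chance that the level meets the six-patient criterion, which is 0.23.
- The plan introduces the 90% interval for the expansion cohort; applying it to six patients is this review's step.
- The scenario percentages depend on the chosen curves. The mean true rate is below 33% on the first six curves, but not on a flat 0.40 curve.

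On fatigue, it can be argued that the exceptions come after the inclusion bullets and open with a contrasting word, so they prevail. If so, the hospitalisation bullet would add nothing, because grade 3 and intolerable grade 2 non-haematologic toxicities are already DLTs. The order of the text does not settle the matter.

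**Conclusion.** The concern holds on both counts. The 33% statement is wrong as written: the rules bound the observed rate at the MTD at 1/6 (16.7%), not the true rate. The figures in steps 2 and 3 of the working need only the binomial model and show that neither 0/6 nor 1/6 rules out 33%. The overall chance of declaring an MTD at or above 33% ranges from 0% to 43% over the assumed curves and should be read only as showing that it need not be small.

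The two fatigue bullets in 5.2 conflict for hospitalised grade 3 episodes of 7 days or less. The overlap is narrow, but a single event can change the MTD. The escalation rules and the printed table are arithmetically sound. The point should be fixed; it does not undermine the design.

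**What to change.** 1. Replace the sentence in 13.1 with: *The rules ensure at most 1 of 6 observed DLTs at the MTD; the true rate may exceed 33% (90% exact CI for 1/6: 0.9%-58%; for 0/6: 0%-39%).*
2. Add to 13.1 that the cycle-1 DLT rate will be reported for all patients treated at the MTD, escalation plus expansion, with the 90% exact interval already planned. State the denominator: 14 if escalation patients at the MTD count toward the 14, or 20 if the 14 are additional.
3. Reconcile the two fatigue bullets in 5.2 before DLTs are scored. Which classification applies is for the investigators and sponsor to decide.
4. As a minor consistency edit, align the CTCAE v4.0 reference in 13.1 with the version 5 references in 5.2, 7.2 and 13.3. No DLT whose classification would change has been identified.

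The cost is one sentence and one reporting line in 13.1, one clarifying line in 5.2 and one version number. The stated property of the MTD becomes less favourable.
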